As standard of care, participants from both arms will return to the laboratory and outpatient clinic at 2 months and 12 months following their studies for review of their CPAP machine. At these times CPAP uptake and adherence and Epworth Sleepiness Score questionnaire will be collected, as standard of care in both arms.

Inclusion and exclusion criteria:

Inclusion criteria

- All treatment naïve patients attending Sleep Disorders Clinic for sleep studies with suspected or proven obstructive sleep apnoea who able to provide informed consent.
- Adult patients (18 years and older).

Exclusion criteria

- Those unable to provide informed consent.
- Patients from non-English speaking background, as video clips will only be provided in English initially.
- Patients less than 18 years old.

Power calculation:

Previous studies have estimated a sample size of 200 patients are required to detect a 1 hour per night increase in CPAP adherence. Assuming an SD of 2.5 hours based on previous observational data and power of 80%, with a two-sided significance level of 0.05, the estimated total sample size is 208 patients¹¹.

End points:

Primary Outcome

The primary outcome of this study is to determine CPAP adherence (hrs) in both standard of care and audio-visual arms at 2-months and 12-months. CPAP counter metres are present in all modern CPAP devices. This is a tamper-proof method whereby machine usage hours are detected by in-device computers and is usually downloaded at clinic follow up.

Secondary Outcomes

- Non-scheduled sleep scientist time (phone calls and clinic consultation) measured in minutes. The Sleep Disorders staff at the Princess Alexandra Hospital already routinely collects this information via the Sleep Disorders database. The Study Co-ordinator will obtain this from the sleep database at 2-months and 12-months.
- CPAP therapy uptake at 2-months and 12-months.

Data collection

Data collection method and storage

A research sleep scientist and the principal investigator [name] will carry out all data collection. All data collected will be de-identified and no personal details of patients will be collected as part of this study.

Data will be collected on to a Microsoft Excel file which will be password protected. The collected data will be stored on a secure Queensland Health computer located at the Department of Respiratory and Sleep Medicine at Princess Alexandra Hospital.

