As per the requirements stated in the Australian Code for the Responsible Conduct of Research, the data will be securely stored for 15 years from the date of completion of the project. If the principle investigator moves on from Queensland Health in that time period, access to the data will be provided to the senior associate investigator.

Data variables

Both groups will have demographic data and a number of internationally validated questionnaires (Epworth Sleepiness Score, quality of life questionnaires, insomnia questionnaires and depression questionnaires) and OSA diagnostic information collected at recruitment and the follow-up periods as outlined above; all of which is current standard of care. CPAP uptake and adherence data will also be downloaded from the CPAP machine and entered into the Sleep Disorders database as per usual practice, and collected as part of the study at the follow-up times.

Analysis

Statistical analysis plan:

The analysis will be carried out on an intention-to-treat principle. Estimated frequencies and proportions for the variables will be calculated in descriptive analysis. The Chi-Squared test will be used to compare the rates and t-test to compare means. The threshold for statistical significance will be established at 5%. Data quality will be assessed after data collection and potentially inform the analytical methods. The analyses will be carried out using Statistical Package for the Social Sciences version 24 (SPSS for Windows, IBM Corporation, Somers, NY, USA).

RISKS

There are no extra risks or disadvantages to patients by taking part in this study. Patients may be requested to stay an extra 30 minutes after their sleep study to watch the videos and complete a questionnaire. Rest of the management is all part of standard care.

TIMELINE

Expected start date: April 2019

Recruitment phase: 12 months

Expected completion date: April 2020

RESEARCH OUTPUTS

Results of this study will predominantly be distributed to the clinical staff involved in immediate care of patients with obstructive sleep apnoea through departmental presentations and internal reports. The results may also be presented at conferences and published in peer reviewed journals relevant to the field.

REFERENCES

1. Reawakening Australia: The economic cost of sleep disorders in Australia. . Sleep Health Foundation, 2011. (Accessed September 2015, at http://www.sleephealthfoundation.org.au/pdfs/news/Reawakening_Australia.pdf.)

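### The primary t-test is valid but gives no role to baseline data the trial collects, and the method may be changed after data collection without masking to arm

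*Protocol*

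**What the plan says.** The primary outcome, under End points, is "CPAP adherence (hrs) in both standard of care and audio-visual arms at 2-months and 12-months". The analysis section states intention to treat and a 5% threshold, and gives the tests: "The Chi-Squared test will be used to compare the rates and t-test to compare means". It names no covariate and no model. The words unadjusted and at each visit do not appear; they are the natural reading of a t-test applied to an outcome measured at two times.

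Data variables lists what is available at recruitment: "Both groups will have demographic data and a number of internationally validated questionnaires", including the Epworth score and insomnia and depression questionnaires, together with OSA diagnostic information.

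The analysis section then adds: "Data quality will be assessed after data collection and potentially inform the analytical methods". It does not say what would trigger a change, what the replacement would be, who decides, or whether that person is masked to arm.

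The Power calculation section sizes the trial to "detect a 1 hour per night increase in CPAP adherence". It continues "Assuming an SD of 2.5 hours based on previous observational data", with 80% power and "with a two-sided significance level of 0.05", and arrives at 208 patients.

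**The concern.** There are two separate weaknesses.

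**Precision.** Baseline variables that predict CPAP use would reduce the residual variance if they entered the primary model. The trial collects such variables as routine care and gives them no role in the named test, so any precision they offer is lost.

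**An open method.** The data-quality sentence loosens the choice of test that the same section has just made. Laboratory staff play the videos, so they know the allocation, and a research sleep scientist and the principal investigator carry out all data collection. Nothing in the protocol separates knowledge of hours by arm from the decision on how to analyse them. If that decision depended on the result, the stated 5% level would no longer be exact. The question is by how much.

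**Working it through.** **1. The plan's own figure.** Inputs from the Power calculation section: difference 1 h, SD 2.5 h, two-sided 0.05, power 80%. Two equal arms follow from the equal number of allocation cards.

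n per arm = 2 × (1.960 + 0.842)² × 2.5² / 1² = 98.1, so 99 per arm and 198 in total. The exact t-test calculation gives 99.08, so 100 per arm and 200 in total.

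The stated 208 (104 per arm) is slightly larger than either. With complete data its power is 82.2% (normal approximation) or 81.9% (t-test). The unadjusted test therefore meets the planned 80%.

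**2. Gain from baseline adjustment.** Let R² be the share of variance in hours explained by the covariates. The documents give no value, so the range is assumed.

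Residual SD = 2.5 × √(1 − R²); equivalent increase in patients = 1/(1 − R²) − 1.

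| Assumed R² | Residual SD (h) | Power at 104 per arm (t-test) | Equivalent extra patients |
|---|---|---|---|
| 0 | 2.500 | 81.9% | – |
| 0.05 | 2.437 | 83.8% | 5% |
| 0.10 | 2.372 | 85.7% | 11% |
| 0.15 | 2.305 | 87.6% | 18% |

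**3. Type I error if the method is chosen by result.** These are simulations with no true effect, 104 per arm and one visit, always taking the smallest p-value. That is the worst case.

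*Set A:* 10,000 runs; hours drawn from a normal distribution with mean 4.2 and SD 2.5, cut off at 0 and 12; R² from 0.05 to 0.20.
- One test fixed in advance, adjusted or not: 5.0-5.3%
- t-test or rank test: 5.6-6.1%
- Adding a covariate-adjusted model to the choice: 6.6-7.7%
- Adding a t-test on users only: 8.0-8.8%

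*Set B:* 20,000 runs; an assumed 30% of patients at zero hours, users' hours normal with mean 4.8 and SD 2.
- t-test alone: 5.0%
- t-test or rank test, all patients: 5.5%
- Adding users only: 9.2%
- Adding a chi-squared test at 4 hours: 10.7%

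The large step in set B comes with the users-only test, which departs from the stated intention-to-treat principle. The 4-hour test replaces the stated endpoint, which is hours. With all patients and the stated endpoint, choosing between the t-test and the rank test costs about 0.5 to 1 percentage point. An adjusted model that is optional rather than fixed adds roughly a further 1 to 2 points.

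**The case against.** The strongest reply is that a t-test fixed in advance is a sound primary analysis of a randomised trial. It holds its level, it matches the unadjusted SD used for the sample size, and it has about 82% power. Patients are treatment naive, so the covariate that usually helps most, a baseline value of the outcome, does not exist. Covariates are also often left to a separate analysis plan, which may exist here. All of this stands, and it makes adjustment an efficiency gain rather than the repair of an error. What remains is that the protocol names a test that leaves collected baseline data unused, and that better precision is available at almost no cost.

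On the open clause, the text speaks of data quality and says only that it may potentially inform the methods. A choice made blind to arm would largely protect the 5% level. Hours come from the device counter, and the protocol does not say who runs the analysis. That also stands, but masking is exactly what the clause omits. This is permission the protocol gives in words, not a silence that another document would naturally fill.

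Three stronger readings are tempting and are not supported:

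- *The 5% level is broken, with a false-positive rate near 9-11%.* Those rates depend on a users-only analysis or a changed endpoint, neither of which the protocol plans, and on choosing by p-value, which it does not announce.
- *The t-test wrongly treats a patient's two visits as unrelated.* Comparing arms at one visit assumes nothing about the other. With complete data, an unadjusted mixed model with free visit means and unstructured covariance gives the same differences at each visit.
- *A two-visit mixed model is needed.* Its gain at 12 months is a variance ratio of 1 − m × ρ². With an assumed loss m of 25% and visit correlation ρ of 0.5 to 0.7, this is 0.94 to 0.88, a 6-12% reduction. It relies on data missing at random, which is doubtful if patients who stop CPAP also stop attending.

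**Conclusion.** The point holds as a modest efficiency gain forgone plus a loosely worded clause. It is not a finding that the primary test is invalid, that the trial is under-powered or that the 5% level has failed.

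Adjustment is worth about 2 to 6 percentage points of power (81.9% to 83.8-87.6%) if the covariates explain 5-15% of the variance. That range is assumed. Without baseline CPAP hours, the lower end is a realistic possibility.

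The open clause exposes the type I error only if the choice depends on results by arm. Within the stated population and endpoint, the worst case is about 5.5-6% for a t-test or rank test, and up to 7.7% if an adjusted model is also among the options. That last figure is a reason to fix the adjusted model in advance rather than leave it available.

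**What to change.** 1. Pre-specify the primary comparison of hours per night as a linear model (ANCOVA) of arm, adjusted for baseline Epworth score, OSA severity, age and sex. Report the adjusted difference with its 95% CI. The protocol mentions demographic data and OSA diagnostic information without itemising them, so the exact variables should be named. A mixed model over both visits may be added as an option, with its missing-at-random assumption stated.

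2. Replace the data-quality sentence with wording such as: *Data quality is reviewed with allocation masked; the primary analysis is not changed after allocation is merged.*

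The adjusted model can be applied at either visit. It does not settle which of the two visits is decisive, which is a separate matter.

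The cost is a few sentences of protocol text, slightly more analysis work in the software already planned, and a stated rule for patients with missing baseline covariates so that they stay in the intention-to-treat comparison. No extra patients or measurements are needed.

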All treatment naïve new case sleep patients attending the SDC will be invited to participate. The sleep laboratory administration staff will send out a study information flyer with the standard appointment confirmation letters. This flyer will invite treatment naïve new case patients to participate in the study. Patients interested will be invited to participate at the end of their initial sleep consultation and provided the Patient Information and Consent Form (PICF) to take home and consider. Additionally as part of the standard telephone confirmation process prior to upcoming sleep studies, sleep laboratory administration staff will offer the option of participation in the trial. Within the sleep database their details will be added to the research participation log.

Study procedure:

When eligible patients return to the sleep laboratory for their CPAP initiation sleep study, consent will be obtained by a research sleep scientist appointed as part of the study. At this point participating patients will be randomised to either Group 1 "Standard of care" or Group 2 "audio-visual clips". Sealed envelopes containing cards method will be used. Equal number of cards for each arm will be placed in opaque envelopes. The envelopes will be placed in a box in a locked cupboard in the sleep laboratory. An independent staff member of sleep laboratory will pick an envelope after consenting the patient.

For patients in Group 1 "Standard of Care" education will be provided at night by the sleep scientists according to standard laboratory policy and procedures. This includes a two-page written patient handout about the study and OSA. The following morning, a sleep physician will review the patient's data and counsel them on the results to implement a management plan (as per standard of care).

For those participants in Group 2 "Audio-visual clips" following their usual sleep study set up, with education from the night sleep scientific staff, a computer will be provided with Video 1 and Video 2 loaded, with assistance from the sleep scientists to play the video. The following morning, the reviewing Sleep Physician will perform data and interventions as standard of care. The participating patients s will stay in the laboratory for an additional 20 minutes to watch video 3, 4 and 5.

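### The stated completion date of April 2020 is only the end of recruitment and leaves no time for the 2-month and 12-month follow-up that the endpoints require

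*Protocol*

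**What the plan says.** The Protocol's TIMELINE section has three lines: "Expected start date: April 2019", "Recruitment phase: 12 months" and "Expected completion date: April 2020". It gives no follow-up period.

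Under End points, the primary outcome is to "determine CPAP adherence (hrs) in both standard of care and audio-visual arms at 2-months and 12-months". Both secondary outcomes (unscheduled sleep scientist time and CPAP uptake) are set at the same two time points, and so are Aims 1 and 2 in the STUDY AIM section.

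The Study procedure section fixes when each patient's clock starts. Consent is taken when the patient comes for the CPAP initiation sleep study, and "At this point participating patients will be randomised to either Group 1" or Group 2. After that, "participants from both arms will return to the laboratory and outpatient clinic at 2 months and 12 months following their studies". The Data variables section adds that uptake and adherence data are downloaded in usual practice and "collected as part of the study at the follow-up times".

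**The concern.** The completion date equals the start date plus the recruitment phase, with nothing added for follow-up. A patient randomised late in recruitment has a 2-month visit about two months after the stated end of the study and a 12-month visit about a year after it. Almost every patient's 12-month visit falls after that end.

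If the study were closed and analysed to this timeline, the 12-month half of the primary outcome would be missing for nearly everyone. The 12-month parts of both aims and both secondary outcomes would go with it, and the 2-month data would be incomplete. The loss would follow enrolment date and not treatment arm, so it should fall on both arms alike. Its main cost would be precision and, at 12 months, having almost no outcome to analyse.

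**Working it through.** **Inputs**
- Start April 2019, recruitment 12 months, completion April 2020 (TIMELINE).
- Visits at 2 and 12 months after the sleep study at which the patient is randomised (Study procedure).
- Planned total 208, difference 1 hour per night, SD 2.5 hours, two-sided 5% level (Power calculation).

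**Step 1: reproduce the stated date.** April 2019 + 12 months of recruitment = April 2020. The stated completion date is obtained only with zero follow-up.

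**Step 2: add the follow-up that the endpoints need.**
- Last 2-month visit: April 2019 + 12 + 2 months = June 2020.
- Last 12-month visit: April 2019 + 12 + 12 months = April 2021, which is 24 months after the start.

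**Step 3: how many patients would have each visit by the stated date.** The protocol gives no accrual curve, so uniform accrual of 208 patients over 12 months is assumed. The share reaching month m is (completion date − m months − start date) / length of recruitment, with a floor of 0. The dates are given by month only, so the days within April are varied. Recruitment lasts 366 days because it spans February 2020.

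| Start | Completion | Reach 12 months | Reach 2 months |
|---|---|---|---|
| 1 April 2019 | 1 April 2020 | 0 | 306/366 = 83.6%, 174 |
| 1 April 2019 | 30 April 2020 | 29/366 = 7.9%, 16 | 334/366 = 91.3%, 190 |
| 15 April 2019 | 1 April 2020 | 0 | 292/366 = 79.8%, 166 |
| 15 April 2019 | 30 April 2020 | 15/366 = 4.1%, 9 | 320/366 = 87.4%, 182 |
| 30 April 2019 | 1 April 2020 | 0 | 277/366 = 75.7%, 157 |
| 30 April 2019 | 30 April 2020 | 0 | 305/366 = 83.3%, 173 |

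So 0 to 16 patients (0-8%) would have a 12-month value and 157 to 190 (76-91%) a 2-month value. That leaves 208 − 190 = 18 to 208 − 157 = 51 patients without even the 2-month value. The lowest 2-month figure pairs the latest start with the earliest end, where recruitment itself would overrun the completion date. It is an outer limit.

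**Step 4: what those numbers would mean for power.** With n per arm, power is approximately Φ(1 / (2.5 × √(2/n)) − 1.96).
- 12 months, best case, n = 8: 1 / (2.5 × 0.5) = 0.80; Φ(0.80 − 1.96) = Φ(−1.16) = 12%.
- 2 months, n = 78.5: Φ(2.51 − 1.96) = 71%.
- 2 months, n = 95: Φ(2.76 − 1.96) = 79%.

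All 208 patients (n = 104) would give 82% by the same formula. Dropout is ignored throughout.

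**The case against.** The strongest reply is that no data need be lost. The dates are labelled as expected, and nothing in the protocol says that collection stops, or that the database is locked, in April 2020. The follow-up text is written per patient, the visits are standard of care, and the devices record usage whatever the study calendar says. This stands. A reader might infer from the timeline that the 12-month outcome cannot be collected, or that the trial is infeasible. The documents do not support that. The loss follows only if the study is actually closed on the stated date.

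A second reply is that completion was meant as completion of recruitment, which would explain why the sum comes out exactly. The protocol does not say so. It lists recruitment and completion as separate lines, and the data-storage text counts the 15-year retention period from completion of the project as a whole. Even on this reading the timeline would give no end date for the study and would still need correcting.

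A third reply is that visit windows, data cleaning and database lock belong in a statistical analysis plan or data management plan. That is right, and their absence is not part of this point. The point concerns a date that the protocol does state and that its own endpoints contradict.

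**Conclusion.** The point holds as an internal contradiction. The stated completion date leaves no follow-up time and falls 12 months short of what the primary outcome, both aims and both secondary outcomes require, and nothing elsewhere in the protocol repairs it. The calendar result (last 12-month visit in about April 2021, last 2-month visit in about June 2020) needs no assumption beyond recruitment running as planned.

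The patient counts are conditional. They assume that the study closes on the stated date and that 208 patients accrue uniformly, and they vary with the days chosen in April: 0-8% with a 12-month value, 76-91% with a 2-month value. A different accrual pattern would shift them. A completion date that early would nonetheless leave the 12-month outcome largely unobserved unless nearly all patients were recruited at the very start. The date should be corrected before anyone plans data collection or analysis by it.

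**What to change.** In the TIMELINE, change the expected completion date to the last patient's 12-month visit, no earlier than about April 2021 (24 months after the start), and show follow-up as a separate line from recruitment. State that the final analysis of the 12-month outcome is done only after that visit.

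The cost is a protocol amendment to the dates and a final result about a year later. No extra visits are needed, because follow-up at 2 and 12 months is already standard of care.

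The endpoints and the recruitment period should stay as they are. Keeping April 2020 by dropping the 12-month primary outcome and stopping recruitment two months early is not a sound alternative. It would leave both secondary outcomes set at 12 months. At uniform accrual it would also yield about 208 × 10/12 = 173 patients against the target of 208.
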